Hypophysitis	2-4	Toxicity resolves to Grade 0-1. Therapy with pembrolizumab can be continued while endocrine replacement therapy is instituted	Toxicity does not resolve within 12 weeks of last dose or inability to reduce corticosteroid to 10 mg or less of prednisone or equivalent per day within 12 weeks
Hyperthyroidism	3	Toxicity resolves to Grade 0-1	Toxicity does not resolve within 12 weeks of last dose or inability to reduce corticosteroid to 10 mg or less of prednisone or equivalent per day within 12 weeks
	4	Permanently discontinue	Permanently discontinue
Hypothyroidism		Therapy with pembrolizumab can be continued while thyroid replacement therapy is instituted	Therapy with pembrolizumab can be continued while thyroid replacement therapy is instituted
2 ^b T Infusion		Toxicity resolves to Grade 0-1	Permanently discontinue if toxicity develops despite adequate premedication
Reaction	3-4	Permanently discontinue	Permanently discontinue
Pneumonitis	neumonitis 2 Toxicity resolves to Grade 0-1		Toxicity does not resolve within 12 weeks of last dose or inability to reduce corticosteroid to 10 mg or less of prednisone or equivalent per day within 12 weeks
	3-4	Permanently discontinue	Permanently discontinue
Nephritis or inabi		Toxicity does not resolve within 12 weeks of last dose or inability to reduce corticosteroid to 10 mg or less of prednisone or equivalent per day within 12 weeks	
	3-4	Permanently discontinue	Permanently discontinue
All Other Drug- Related Toxicity ^c	3 or Severe	Toxicity resolves to Grade 0-1	Toxicity does not resolve within 12 weeks of last dose or inability to reduce corticosteroid to 10 mg or less of prednisone or equivalent per day within 12 weeks
	4	Permanently discontinue	Permanently discontinue

Note: Permanently discontinue for any severe or Grade 3 drug-related AE that recurs or any life-threatening event.

In case toxicity does not resolve to Grade 0-1 within 12 weeks after last infusion, trial treatment should be discontinued after consultation with the Sponsor Investigator. Subjects who require corticosteroids to manage drug-related adverse events must be at an equivalent dose of ≤10mg per day of prednisone to resume dosing with pembrolizumab. Furthermore, an inability to reduce

^a For patients with liver metastasis who begin treatment with Grade 2 AST or ALT, if AST or ALT increases by greater than or equal to 50% relative to baseline and lasts for at least 1 week then patients should be discontinued.

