Uncomplicated Diarrhea, ¹ Grade 1 or 2	 Diet: Stop all lactose containing products; eat small meals, BRAT-diet (banana, rice, apples, toast) recommended. Hydration: 8-10 large glasses of clear liquids per day (e.g., Gatorade or broth). Loperamide³: Initially 4 mg, followed by 2 mg every 4 hours or after every unformed stool; maximum 16 mg/day. Continue until diarrhea- free for 12 hours. Diarrhea >24 hours: Loperamide 2 mg every 2 hours; maximum 16 mg/day. Consider adding oral antibiotics. Diarrhea >48 hours: Loperamide 2 mg every 2 hours; maximum 16 mg/day. Add budesonide or other second-line therapies (otreotide, or tincture of opium) and oral antibiotics. 	 Continue trametinib. If diarrhea is grade 2 for > 48h, interrupt trametinib until diarrhea resolves to grade ≤1. Restart trametinib at the same dose level If treatment delay is > 28 days, discontinue trametinib.
Uncomplicated Diarrhea, ¹ Grade 3 or 4 Any Complicated Diarrhea2	 Clinical evaluation mandatory. Loperamide³: Initially 4 mg, followed by 2 mg every 4 hours or after every unformed stool; maximum 16 mg/day. Continue until diarrhea- free for 12 hours. Oral antibiotics and second-line therapies if clinically indicated Hydration: Intravenous fluids if clinically indicated. Antibiotics (oral or intravenous) if clinically indicated. Intervention should be continued until the subject is diarrhea-free for ≥24 hours. Intervention may require hospitalization for subjects at risk of life- threatening complications. 	 Interrupt trametinib and pembrolizumab until diarrhea resolves to ≤ grade 1. Then restart pembrolizumab and trametinib reduced by one dose level.⁴ If 3 dose reductions of study treatment are clinically indicated, permanently discontinue trametinib. If treatment delay is >28 days, discontinue trametinib and pembrolizumab.

¹ Uncomplicated diarrhea defined by the absence of symptoms such as cramping, nausea/vomiting, ≥ grade 2, decreased performance status, pyrexia, sepsis, neutropenia ≥ grade 3, frank bleeding, and/or dehydration requiring intravenous fluid substitution

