5.5 Concomitant Medications/Vaccinations (allowed & prohibited)

Medications or vaccinations specifically prohibited in the exclusion criteria are not allowed during the ongoing trial. If there is a clinical indication for one of these or other medications or vaccinations specifically prohibited during the trial, discontinuation from trial therapy or vaccination may be required. The investigator should discuss any questions regarding this with the Merck Clinical team. The final decision on any supportive therapy or vaccination rests with the investigator and/or the subject's primary physician.

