5.5.2 Prohibited Concomitant Medications

Subjects are prohibited from receiving the following therapies during the Screening and Treatment Phase of this trial:

- Antineoplastic systemic chemotherapy or biological therapy
- Immunotherapy not specified in this protocol
- Chemotherapy not specified in this protocol
- Investigational agents other than pembrolizumab
- Radiation therapy
 Note: Radiation therapy to a symptomatic solitary lesion or to the brain may be allowed at the investigator's discretion.
- Live vaccines within 30 days prior to the first dose of trial treatment and while participating in the trial. Examples of live vaccines include, but are not limited to, the following: measles, mumps, rubella, varicella/zoster, yellow fever, rabies, BCG, and typhoid vaccine.
- Systemic glucocorticoids for any purpose other than to modulate symptoms from an event of clinical interest of suspected immunologic etiology. The use of physiologic doses of corticosteroids may be approved after consultation with the Investigator.

Subjects who, in the assessment by the investigator, require the use of any of the aforementioned treatments for clinical management should be removed from the trial. Subjects may receive other medications that the investigator deems to be medically necessary.

The Exclusion Criteria describes other medications which are prohibited in this trial.

There are no prohibited therapies during the Post-Treatment Follow-up Phase.

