5.6 Rescue Medications & Supportive Care

5.6.1 Supportive Care Guidelines

5.6.2 Pembrolizumab

Subjects should receive appropriate supportive care measures as deemed necessary by the treating investigator. Suggested supportive care measures for the management of adverse events

with potential immunologic etiology are outlined below. Where appropriate, these guidelines include the use of oral or intravenous treatment with corticosteroids as well as additional anti-inflammatory agents if symptoms do not improve with administration of corticosteroids. Note that several courses of steroid tapering may be necessary as symptoms may worsen when the steroid dose is decreased. For each disorder, attempts should be made to rule out other causes such as metastatic disease or bacterial or viral infection, which might require additional supportive care. The treatment guidelines are intended to be applied when the investigator determines the events to be related to pembrolizumab.

Note: if after the evaluation the event is determined not to be related, the investigator does not need to follow the treatment guidance (as outlined below). Refer to Section 5.2.1 for dose modification.

It may be necessary to perform conditional procedures such as bronchoscopy, endoscopy, or skin photography as part of evaluation of the event.

• Pneumonitis:

- For Grade 2 events, treat with systemic corticosteroids. When symptoms
 improve to Grade 1 or less, steroid taper should be started and continued over no
 less than 4 weeks.
- o For **Grade 3-4 events**, immediately treat with intravenous steroids. Administer additional anti-inflammatory measures, as needed.
- Add prophylactic antibiotics for opportunistic infections in the case of prolonged steroid administration.

• Diarrhea/Colitis:

Subjects should be carefully monitored for signs and symptoms of enterocolitis (such as diarrhea, abdominal pain, blood or mucus in stool, with or without fever) and of bowel perforation (such as peritoneal signs and ileus).

- O All subjects who experience diarrhea/colitis should be advised to drink liberal quantities of clear fluids. If sufficient oral fluid intake is not feasible, fluid and electrolytes should be substituted via IV infusion. For Grade 2 or higher diarrhea, consider GI consultation and endoscopy to confirm or rule out colitis.
- o For Grade 2 colitis, administer oral corticosteroids.
- For Grade 3 or 4 colitis, treat with intravenous steroids followed by high dose oral steroids.

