7.2.3.2 Events of Clinical Interest

Selected non-serious and serious adverse events are also known as Events of Clinical Interest (ECI) and must be reported within 24 hours to the Sponsor Investigator and within 2 working days to Merck Global Safety. (Attn: Worldwide Product Safety; [contact]).

For the time period beginning when the consent form is signed until treatment allocation/randomization, any ECI, or follow up to an ECI, that occurs to any subject must be reported within 24 hours to the Sponsor Investigator and within 2 working days to Merck Global Safety if it causes the subject to be excluded from the trial, or is the result of a protocol-specified intervention, including but not limited to washout or discontinuation of usual therapy, diet, placebo treatment or a procedure.

For the time period beginning at treatment allocation/randomization through 90 days following cessation of treatment, or 30 days following cessation of treatment if the subject initiates new anticancer therapy, whichever is earlier, any ECI, or follow up to an ECI, whether or not related to Merck product, must be reported within 24 hours to the Sponsor Investigator and within 24 hours to Merck Global Safety.

Events of clinical interest for this trial include:

1. an overdose of Merck product, as defined in Section 7.2.1 - Definition of an Overdose for This Protocol and Reporting of Overdose to the Sponsor Investigator, that is not associated with clinical symptoms or abnormal laboratory results.

2. an elevated AST or ALT lab value that is greater than or equal to 3X the upper limit of normal and an elevated total bilirubin lab value that is greater than or equal to 2X the upper limit of normal and, at the same time, an alkaline phosphatase lab value that is less than 2X the upper limit of normal, as determined by way of protocol-specified laboratory testing or unscheduled laboratory testing.*

*Note: These criteria are based upon available regulatory guidance documents. The purpose of the criteria is to specify a threshold of abnormal hepatic tests that may require an additional evaluation for an underlying etiology.

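### Section 8.0 restricts the safety analysis to patients who received both drugs, so a patient whose toxicity ends treatment during the single-drug lead-in drops out of the reported safety rates

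*Combined protocol and SAP*

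**What the plan says.** **Safety set.** Section 8.0 names the patients to be analysed for safety and efficacy as those who receive a dose of pembrolizumab and of trametinib. No other sentence in the plan defines a safety population. The next sentence replaces anyone who leaves before reaching the combination, whatever the reason. A little later, Section 8.0 says that patients taken off for unacceptable treatment-related events are followed up but not replaced. Section 5.9, which is headed as the replacement strategy, is marked not applicable.

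**Lead-in.** Under Section 5.2, Arm A receives trametinib alone in cycle 1 and Arm B receives pembrolizumab alone. The second drug starts on day 1 of cycle 2 in both arms.

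**What safety is for.** The hypothesis in Section 3.1 is that the combination, given in the lead-in and intermittent schemes, is safe and tolerable. Section 2.1 makes safety profile one of the criteria for choosing the arm to develop.

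**Steroids (minor note).** Section 5.5.2 prohibits "Systemic glucocorticoids for any purpose other than to modulate symptoms from an event of clinical interest of suspected immunologic etiology" and says that subjects who "require the use of any of the aforementioned treatments for clinical management should be removed from the trial". The list in Section 7.2.3.2 ("Events of clinical interest for this trial include") has two entries: symptom-free overdose and a liver laboratory pattern.

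**The concern.** A patient who starts the lead-in drug, has a toxicity that ends treatment and never receives the second drug is not in the safety set as written. Early stops for toxicity are among the most informative events for tolerability, and here they are removed because of their outcome. The effect can only be favourable: the reported rate of such stops is zero however many occur.

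The loss falls on the one period in which the arms differ by design. From cycle 2 both arms receive the same two drugs, so a contrast in safety between the sequences rests partly on cycle 1. If one lead-in drug drives more patients off treatment than the other, the reported comparison would not show it.

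**Working it through.** **1. The plan's own safety figure.** Section 8.0 states at least an 81% chance of seeing one or more cases of an adverse event with a 10% rate in 16 patients. 1 − 0.90^16 = 0.815, so it reproduces. It assumes that every affected patient is counted, and is not itself in dispute.

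**2. Is the patient in the safety set?** Section 8.0 requires a dose of each drug. Section 5.2 gives only one drug in cycle 1. A patient whose treatment ends in cycle 1 has had one drug and is therefore outside the set.

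**3. Does the DLT analysis recover the patient?** The text points both ways.

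| Place | Bearing on a lead-in toxicity stop |
|---|---|
| 5.4, first paragraph | DLT evaluability requires a completed lead-in and concurrent receipt of both drugs: not counted |
| 8.0, first paragraph | Escalation uses DLTs seen in Cycle 2: not counted |
| 5.4, second paragraph | A DLT is a qualifying event in the first two cycles (6 weeks): could be counted |
| 5.4, 80% clause | Names only unrelated events as grounds for non-evaluability: related stops might count |
| 5.4, interruption criterion | Refers to Cycle 1: could be counted |

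The DLT analysis may capture such a patient, but cannot be relied on to do so. It also applies only to dose escalation, so it offers nothing for the expansion cohorts of 12.

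**4. Effect of one lead-in toxicity stop in an expansion arm.** Rates are for treatment ended by lead-in toxicity, with exact (Clopper-Pearson) 95% intervals; for 0/n the upper limit is 1 − 0.025^(1/n).

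| Replacement | Reported under 8.0 | All treated |
|---|---|---|
| Replaced | 0/12 (0 to 26.5%) | 1/13 = 7.7% (0.2 to 36.0%) |
| Not replaced | 0/11 (0 to 28.5%) | 1/12 = 8.3% (0.2 to 38.5%) |

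The omission arises under either replacement rule; only the denominators change.

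**5. How likely is at least one omission?** The documents give no lead-in stop rate, so the rate p is assumed. With no other early stops, the chance per arm is 1 − (1 − p)^12. This holds both for 12 starters without replacement and for accrual until 12 are analysed.

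- p = 2%: 1 − 0.98^12 = 21.5%
- p = 5%: 1 − 0.95^12 = 46.0%
- p = 10%: 1 − 0.90^12 = 71.8%

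Over both arms the exponent is 24, giving 38.4%, 70.8% and 92.0%.

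**6. Sensitivity to other early stops.** If patients who leave early for any reason are replaced, more patients start and the chance rises. With 5% toxicity stops and an assumed 10% other stops it is 1 − (0.85/0.90)^12 = 49.6%, against 46.0% in step 5.

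**The case against.** **The combination is the stated target.** The objective sentence in Section 3.1 concerns pembrolizumab given together with trametinib, and Section 5.4 says that escalation assesses the combination after the lead-in. A set limited to combination-treated patients is therefore partly deliberate. That justifies the DLT rule and a combination-period summary. It does not justify having no summary that includes the lead-in, since the hypothesis and the arm selection both take in the whole scheme.

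**The events are not lost to oversight.** Section 7.2 collects all adverse events from allocation, Section 7.2.3.1 requires prompt reporting of serious ones, and Section 10.5 has them discussed at regular meetings. Section 8.0 also bases the RP2D on toxicities observed in the study, and its adverse event summary restates no population. All of this stands. A reader might infer that lead-in toxicity goes unmonitored, or that the adverse event summary is the only analysis that could show it. The documents support neither, given the DLT text in step 3. What is missing is a place in the defined safety set.

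**Replacement may be settled.** The sentence denying replacement comes after the other two and can be read as an exception for treatment-related stops. That is plausible but not stated. On that reading the contrast is 0/11 against 1/12, and the omission remains.

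**The patients may be few.** The lead-in is a single cycle of one drug, with trametinib given on at most 10 of 21 days. A patient who stops only trametinib, for example for retinal vein occlusion, can still go on to pembrolizumab and would be counted. Both limits are fair, and no rate is claimed.

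**Steroids.** A reader might infer that Section 5.5.2 forces out most patients with immune toxicity. The rest of the protocol says otherwise. For pneumonitis, Section 5.6.2 directs: "For Grade 2 events, treat with systemic corticosteroids". Section 5.2.1.2 plans for resuming pembrolizumab ("Subjects who require corticosteroids to manage drug-related adverse events must be at an equivalent dose of" 10 mg prednisone per day or less). Section 5.5 adds: "The final decision on any supportive therapy or vaccination rests with the investigator". The intent is clear, and no effect on results is shown.

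**Conclusion.** The point holds for the safety set. As written, Section 8.0 leaves out of the reported safety rates any patient whose toxicity ends treatment before the second drug, and the DLT rules do not dependably bring that patient back. In an arm of 12, each such stop is about 8 percentage points of the all-treated rate, reported as zero. The intervals in step 4 overlap almost entirely, so the harm is not a large numerical shift. It is that a class of tolerability failure cannot appear in the table, in a trial whose primary question is tolerability.

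The chances of 21.5%, 46.0% and 71.8% rest on assumed stop rates and on no other early departures. They are illustrations and should not be read as upper bounds: step 6 gives a higher figure at the same toxicity rate. The conclusion itself needs no stop rate, since it follows from Sections 5.2 and 8.0. It is worth correcting before analysis. The steroid wording adds nothing to it beyond a minor drafting note.

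**What to change.** In Section 8.0:

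- Define the safety set as every patient who receives any dose of either drug, whether or not later replaced.
- Summarise adverse events and stops for toxicity by arm, with the lead-in and combination periods shown separately.
- State one replacement rule for lead-in stops due to treatment-related toxicity, and repeat it in Section 5.9.

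The cost is wording only. Section 7.2 already collects these events, so no visits, data items or patients are added. The drawback is that the safety denominator will include some patients exposed to one drug only and may differ from the efficacy denominator; separate periods keep this visible.

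Optionally, as a minor clean-up, reword the exception in Section 5.5.2 to cover any adverse event of suspected immune origin and any event for which the protocol itself directs or allows steroids.

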5.6 Rescue Medications & Supportive Care

5.6.1 Supportive Care Guidelines

5.6.2 Pembrolizumab

Subjects should receive appropriate supportive care measures as deemed necessary by the treating investigator. Suggested supportive care measures for the management of adverse events

with potential immunologic etiology are outlined below. Where appropriate, these guidelines include the use of oral or intravenous treatment with corticosteroids as well as additional anti-inflammatory agents if symptoms do not improve with administration of corticosteroids. Note that several courses of steroid tapering may be necessary as symptoms may worsen when the steroid dose is decreased. For each disorder, attempts should be made to rule out other causes such as metastatic disease or bacterial or viral infection, which might require additional supportive care. The treatment guidelines are intended to be applied when the investigator determines the events to be related to pembrolizumab.

Note: if after the evaluation the event is determined not to be related, the investigator does not need to follow the treatment guidance (as outlined below). Refer to Section 5.2.1 for dose modification.

It may be necessary to perform conditional procedures such as bronchoscopy, endoscopy, or skin photography as part of evaluation of the event.

• Pneumonitis:

- For Grade 2 events, treat with systemic corticosteroids. When symptoms
 improve to Grade 1 or less, steroid taper should be started and continued over no
 less than 4 weeks.
- o For **Grade 3-4 events**, immediately treat with intravenous steroids. Administer additional anti-inflammatory measures, as needed.
- Add prophylactic antibiotics for opportunistic infections in the case of prolonged steroid administration.

• Diarrhea/Colitis:

Subjects should be carefully monitored for signs and symptoms of enterocolitis (such as diarrhea, abdominal pain, blood or mucus in stool, with or without fever) and of bowel perforation (such as peritoneal signs and ileus).

- O All subjects who experience diarrhea/colitis should be advised to drink liberal quantities of clear fluids. If sufficient oral fluid intake is not feasible, fluid and electrolytes should be substituted via IV infusion. For Grade 2 or higher diarrhea, consider GI consultation and endoscopy to confirm or rule out colitis.
- o For Grade 2 colitis, administer oral corticosteroids.
- For Grade 3 or 4 colitis, treat with intravenous steroids followed by high dose oral steroids.
- When symptoms improve to Grade 1 or less, steroid taper should be started and continued over no less than 4 weeks.

- Type 1 diabetes mellitus (if new onset, including diabetic ketoacidosis [DKA]) or Grade ≥3 Hyperglycemia, if associated with ketosis (ketonuria) or metabolic acidosis (DKA)
 - o For **T1DM** or **Grade 3-4** Hyperglycemia
 - Insulin replacement therapy is recommended for Type I diabetes mellitus and for Grade 3-4 hyperglycemia associated with metabolic acidosis or ketonuria.
 - Evaluate patients with serum glucose and a metabolic panel, urine ketones, glycosylated hemoglobin, and C-peptide.

• Hypophysitis:

- For Grade 2 events, treat with corticosteroids. When symptoms improve to Grade 1 or less, steroid taper should be started and continued over no less than 4 weeks.
 Replacement of appropriate hormones may be required as the steroid dose is tapered.
- o For Grade 3-4 events, treat with an initial dose of IV corticosteroids followed by oral corticosteroids. When symptoms improve to Grade 1 or less, steroid taper should be started and continued over no less than 4 weeks. Replacement of appropriate hormones may be required as the steroid dose is tapered.

• Hyperthyroidism or Hypothyroidism:

Thyroid disorders can occur at any time during treatment. Monitor patients for changes in thyroid function (at the start of treatment, periodically during treatment, and as indicated based on clinical evaluation) and for clinical signs and symptoms of thyroid disorders.

- o **Grade 2** hyperthyroidism events (and **Grade 2-4** hypothyroidism):
 - In hyperthyroidism, non-selective beta-blockers (e.g. propranolol) are suggested as initial therapy.
 - In hypothyroidism, thyroid hormone replacement therapy, with levothyroxine or liothyroinine, is indicated per standard of care.
- Grade 3-4 hyperthyroidism
 - Treat with an initial dose of IV corticosteroid followed by oral corticosteroids. When symptoms improve to Grade 1 or less, steroid taper should be started and continued over no less than 4 weeks. Replacement of appropriate hormones may be required as the steroid dose is tapered.

UCDCC#259 v.Original (05/09/2017)

Products: Pembrolizumab/Trametinib

• Hepatic:

- o For **Grade 2** events, monitor liver function tests more frequently until returned to baseline values (consider weekly).
 - Treat with IV or oral corticosteroids
- o For **Grade 3-4** events, treat with intravenous corticosteroids for 24 to 48 hours.
- o When symptoms improve to Grade 1 or less, a steroid taper should be started and continued over no less than 4 weeks.

• Renal Failure or Nephritis:

- o For Grade 2 events, treat with corticosteroids.
- o For **Grade 3-4** events, treat with systemic corticosteroids.
- When symptoms improve to Grade 1 or less, steroid taper should be started and continued over no less than 4 weeks.
- Management of Infusion Reactions: Signs and symptoms usually develop during or shortly after drug infusion and generally resolve completely within 24 hours of completion of infusion.

Table 16 below shows treatment guidelines for subjects who experience an infusion reaction associated with administration of pembrolizumab (MK-3475). May follow institutional guidelines.

Table 16. Infusion Reaction Treatment Guidelines

NCI CTCAE Grade	Treatment	Premedication at subsequent dosing
Grade 1 Mild reaction; infusion interruption not indicated; intervention not indicated	Increase monitoring of vital signs as medically indicated until the subject is deemed medically stable in the opinion of the investigator, or per institutional policies.	None
Grade 2 Requires infusion interruption but responds promptly to symptomatic treatment (e.g., antihistamines, NSAIDS, narcotics, IV fluids); prophylactic medications indicated for < =24 hrs	Stop Infusion and monitor symptoms. Additional appropriate medical therapy may include but is not limited to: IV fluids Antihistamines NSAIDS Acetaminophen Narcotics Increase monitoring of vital signs as medically indicated until the subject is deemed medically stable in the opinion of the investigator. If symptoms resolve within one hour of stopping drug infusion, the infusion may be restarted at 50% of the original infusion rate (e.g., from 100 mL/hr to 50 mL/hr). Otherwise dosing will be held until symptoms resolve and the subject should be premedicated for the next scheduled dose. Subjects who develop Grade 2 toxicity despite adequate premedication should be permanently discontinued from further trial treatment administration.	Subject may be premedicated 1.5h (±30 minutes) prior to infusion of pembrolizumab (MK-3475) with: Diphenhydramine 50 mg po (or equivalent dose of antihistamine). Acetaminophen 500-1000 mg po (or equivalent dose of antipyretic).
Grades 3 or 4 Grade 3: Prolonged (i.e., not rapidly responsive to symptomatic medication and/or brief interruption of infusion); recurrence of symptoms following initial improvement; hospitalization indicated for other clinical sequelae (e.g., renal impairment, pulmonary infiltrates) Grade 4: Life-threatening; pressor or ventilatory support indicated	Stop Infusion. Additional appropriate medical therapy may include but is not limited to: IV fluids Antihistamines NSAIDS Acetaminophen Narcotics Oxygen Pressors Corticosteroids Epinephrine Increase monitoring of vital signs as medically indicated until the subject is deemed medically stable in the opinion of the investigator. Hospitalization may be indicated. Subject is permanently discontinued from further trial treatment administration.	No subsequent dosing

Appropriate resuscitation equipment should be available in the room and a physician readily available during the period of drug administration.

